19.1 Laboratory trials sample size

For laboratory trials, estimations of the sample size required are dependent on the variability of PE between individuals. As such, a range of sample sizes were calculated that took both this, and variability in the confidence intervals around the estimate, into consideration (Table 3). A conservative estimate of the PE standard deviation of 30 % was chosen, which when allowing for a confidence interval of ± 15 % around the estimate, gives a sample of 16 people. When allowing for 5 % loss-to-follow-up, the total sample size will be 17 people. Equal numbers of male and female participants are preferred.

Table 3. Estimation of sample size for determining the Protective Efficacy of repellent products in laboratory trials.

		Standard deviation of Protective Efficacy					
		10 %	15 %	20 %	25 %	30 %	35 %
Margin of error (CI)	5 %	16	35	62	97	139	189
	10 %	4	9	16	25	35	48

	15 %	2	4	7	11	16	21
	20 %	1	3	4	7	9	12

For stage two laboratory trials (repellent product persistence), multiple follow-ups on the same individuals will generate more repeat data points. As such, the sample size requirement for PE will be sufficient. If we observe in stage one that variability between individuals was much greater than expected then we will consider increasing the sample size for stage two.

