26.3.3 Median Effective Dose (ED₅₀) and Median Effective Time (ET₅₀)

ED₅₀ and ET₅₀ will be calculated in stage two ('persistence') laboratory trials, however, as only one dosage level will be used in the field only ET₅₀ will be estimated there.

The relationship between Protective Efficacy and repellent dose and time since treatment can be estimated using a probit-plane regression model (Equation 2). The coefficient b_1 provides an estimate of the effect of repellent dose on p , and b_2 provides the effect of the time since treatment on p .

Once these coefficients have been estimated, then we can estimate the ED₅₀, concentration (dose) of repellent product that affords 50 % protection from fly contacts at time zero (the time of application). This is done by setting $p=0.5$ and $t_1=0$ and then solving equation 2. We can also estimate ET₅₀, estimating the persistence of the protective effect of a repellent product for a given dosage, using the same method.

Equation 2. Probit-plane regression model for ED₅₀ and ET₅₀

$$\ln [p / (1 - p)] = a + b_1(D_0) + b_2 t_1$$

Where:

- p is as above, estimated from
 - Total duration of fly-arm contact (laboratory trials)
 - Total frequency of fly-eye contacts (field trials)
- D_0 is the dose calculated as the natural logarithm of the dose applied ($\ln[\text{dose}]$)
- t is the time post-treatment in hours
- a , b_1 and b_2 are coefficients estimated using the probit-plane regression model

In the laboratory trials, p will be estimated by the total duration of fly-arm contact, while in the field trials p will be estimated using the total frequency of fly-eye contacts, as defined in section 26.3.1.

27 Monitoring

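### Stage 2 precision rests on repeat readings from the same 17 people, and the ED50/ET50 model has no participant term and no stated interval method

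*Combined protocol and SAP*

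**What the plan says.** Section 19.1 sizes the laboratory trial on person-to-person spread: "estimations of the sample size required are dependent on the variability of PE between individuals". It continues: "A conservative estimate of the PE standard deviation of 30 % was chosen". That, "allowing for a confidence interval of ± 15 % around the estimate, gives a sample of 16 people". Then: "When allowing for 5 % loss-to-follow-up, the total sample size will be 17 people".

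For stage 2 (persistence) there is no calculation for ET50, ED50 or complete protection time. The justification is that "multiple follow-ups on the same individuals will generate more repeat data points. As such, the sample size requirement for PE will be sufficient". One contingency follows: if stage 1 shows much more variation between people than expected, "we will consider increasing the sample size for stage two".

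Section 26.3.3 models ln[p/(1 − p)] as a + b1·ln(dose) + b2·time, where a, b1 and b2 "are coefficients estimated using the probit-plane regression model". ED50 and ET50 are obtained by setting p = 0.5 and solving. The same equation serves the field data for ET50. No section mentions a participant effect, a robust or clustered standard error, resampling by person, or any interval method for these two quantities.

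ED50 and ET50 are secondary outcomes (17.2) and the stated means of comparing product effectiveness (12.2). Persistence estimates inform the choice of products for the field trial (13.1).

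**The concern.** Each person contributes a series of readings. A topical product at one dose gives a reading at time zero and then hourly for six hours (21.1.3.2), so seven. A laboratory wearable repeats that series weekly for four weeks (21.1.4), so about 35. A field child gives six on the first day (21.2.3, 21.2.4).

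These readings are correlated for two reasons.

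- Protective efficacy differs between people. Table 3 assumes this, with an SD of 30 points for a quantity already expressed relative to the person's own control. The within-subject design therefore does not remove it.
- As 21.1.3.2 and 26.3.1 read, one ten-minute control value C is the denominator for every test reading in a session, so an error in C enters all of them.

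More readings per person reduce reading-to-reading noise but not the person-to-person part, and that part largely fixes where the dose-time curve sits. A fit that treats every reading as independent would report more precision for ED50 and ET50 than 17 people, or one field arm, can give.

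**Working it through.** **1. The plan's own figure.** Inputs from 19.1: SD 30, margin ±15. The confidence level is not stated; I assume 95 % two-sided, which reproduces all of Table 3. n = (1.96 × 30 / 15)² = 15.37, so 16; 16 / 0.95 = 16.8, so 17. For protective efficacy at one time point, 17 people give ±1.96 × 30 / √17 = ±14.3 points (±15.4 with the t distribution on 16 df). The figure reproduces.

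**2. What the repeat readings are worth.** With m readings per person and intraclass correlation ICC, the design effect for an overall mean is 1 + (m − 1) × ICC. For m = 7 and 17 people, 17 × 7 = 119 readings:

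| ICC (assumed) | Design effect | Equivalent independent readings |
|---|---|---|
| 0.1 | 1.6 | 74 |
| 0.3 | 2.8 | 43 |
| 0.5 | 4.0 | 30 |
| 0.7 | 5.2 | 23 |

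For a laboratory wearable (m = 35, 595 readings), ICC 0.5 gives a design effect of 18 and about 33 equivalent readings.

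The shared control alone can produce correlation of this order. To first order, logit p varies with ln C − ln T. If ln C and ln T have equal, independent error (an assumption), two readings from one session correlate at var(ln C) / [var(ln C) + var(ln T)] = 0.5, even when people do not differ.

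**3. Coverage of a single-product laboratory ET50 interval.** I took Equation 2 as printed (logit form), at one dose, with 17 people and hours 0 to 6, and assumed a = 1.2, b2 = −0.3 per hour and residual SD 1 on the logit scale. ET50 = −a/b2 = 4 h. Intervals use the delta method, with 4,000 simulated datasets per row.

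| Participant SD | ICC = SD²/(SD² + 1) | Coverage, independent readings | Clustered SE / ordinary SE |
|---|---|---|---|
| 0.5 | 0.20 | 86 % | 1.4 |
| 1.0 | 0.50 | 76 % | 1.8 |
| 1.5 | 0.69 | 73 % | 2.0 |

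Participant-clustered intervals with t on 16 df cover about 96 % throughout.

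**4. Other settings.** Here the total logit SD is held at 1.2 (about 30 points near 50 % efficacy), ET50 is 4 h, the dose slope is 1.0 per ln(dose), and doses run from 1.25 to 20 %. All are assumed. Coverage of the independent-reading 95 % interval:

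| Quantity | ICC 0.1 | 0.3 | 0.5 | 0.7 |
|---|---|---|---|---|
| Laboratory ET50, one dose | 90 % | 82 % | 74 % | 66 % |
| Laboratory ET50, five doses | 76 % | 55 % | 46 % | 38 % |
| Laboratory ED50, five doses | 85 % | 69 % | 62 % | 53 % |
| Laboratory ED50, two high doses only | 94 % | 95 % | 95 % | 96 % |
| Field ET50, 23 children, 6 readings | 93 % | 88 % | 84 % | 78 % |

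Participant clustering restores about 95 % in every row where coverage falls. In the two-high-dose row, which extrapolates downwards to ED50, the ordinary interval is not too narrow.

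**5. Two products compared in the laboratory.** All participants test all products. Under the step 3 assumptions, with equal true ET50 and intervals that ignore pairing, coverage for the ET50 difference is 98 %, 99.7 % and 99.9 % (ICC 0.20, 0.50, 0.69) when all person variation is common to both products. It is 94 to 95 % when three quarters is common, and between about 87 % and 74 % when none is. The documents do not say how much is shared.

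**The case against.** The strongest reply is that Equation 2 describes a mean, not a variance. Clustered or bootstrap intervals are compatible with it, and nothing in the plan says readings will be treated as independent. That is correct, so the statement about width has to be conditional. It does not dispose of the point: the only model given omits the participant, and no variance method is supplied.

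A second reply is that 19.1 is worded for protective efficacy and does not turn readings into people. The number stays at 17, adequate for efficacy at one time point (step 1), and it may be raised. This also stands, so a reader should not infer that the plan counts readings as extra participants. The contingency, however, responds to larger variation between people, not to correlation within them, and the efficacy calculation does not carry over to ET50 or ED50.

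A reader might also infer that product differences will be overstated. The documents do not support that. In a fully crossed design, person effects shared by products cancel, so an analysis ignoring them can give intervals for differences that are too wide (step 5). Clustering of this kind affects the standard errors, not the size of the estimated differences.

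Nor do the documents show that the wrong products would go to the field. Section 13.1 says persistence estimates guide selection but gives no test or interval rule. The primary endpoint, protective efficacy, does not use Equation 2.

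**Conclusion.** The point holds as a conditional one. The stage 2 sample size is supported only by repeat readings on the same people, and the stated ED50/ET50 model neither includes the participant nor comes with an interval method. If it is fitted as written with ordinary standard errors, single-product ET50 intervals are too narrow at every non-zero ICC examined: about 86 % down to 73 % actual coverage in the laboratory for ICC 0.2 to 0.7, with the field affected in the same direction but less. ED50 intervals are too narrow when all five doses enter, but not when only two high doses do. Because 21.1.3.2 admits to stage 2 only doses reaching 30 % efficacy, either situation could arise.

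The ICC, residual SD, intercept and slopes are assumptions, so the coverage figures show direction and range, not expected values for this trial. Comparisons between products in the laboratory would have misstated precision, in a direction that cannot be determined from the documents. The effect is on named secondary outcomes that inform product selection. It should be corrected before the stage 2 analysis, and it does not touch the primary endpoint.

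**What to change.** In 26.3.3, fit Equation 2 with a participant random intercept (and a random time slope if the data support it), or keep the equation and use participant-clustered standard errors or a bootstrap that resamples whole participants. Apply this to laboratory and field data, and state how intervals for ED50 and ET50 are derived. When laboratory products are compared, keep each participant's readings on all products together so that the pairing is used.

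In 19.1, replace the sentence on repeat data points with a statement that precision at each time point is that of 17 participants and that repeat readings do not add independent units. A short table of the expected ET50 and ED50 precision from 17 people over a range of ICC would complete the justification.

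The cost is analysis and justification wording only, with no new participants, visits or measurements. Reported single-product intervals become wider.

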19.2 Field trials sample size

This trial will be powered to detect a protective effect in the intervention (treatment) groups relative to the control groups. To test for 30 % protection (PE) in the intervention arm versus the control arm, assuming a standard deviation of 30% and using 90 % power, 23 children are required in each study group. When allowing for 25 % loss-to-follow-up, the total sample size in each study arm will be 29 people. Equal numbers of male and female participants are preferred.

Not all approximately participants in the wearable repellent device arms of the field trial will be interviewed for intervention acceptability. Based on previous experience, we anticipate that a sample of 15 to 20 child-caregiver pairs, purposively sampled to represent the range of child ages will be sufficient, and further data collection unlikely to yield additional information. However, we will review our data regularly during the data collection process and will adjust the sample accordingly.

20 Enrolment, randomisation and allocation

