13.2 Field trial

In the field clinical trial, eligible participants will be randomised between groups (study arms), each of which will test only one topical repellent or slow-release wearable repellent device, at one concentration. A maximum of four groups will be tested in addition to a control group, and each group will contain 29 children between the ages of three and 12 years. The additional control group, receiving no product, will allow for temporal comparison of fly contact across a day of testing.

The combination of product and product format to be tested will be determined before the study commences. The PE will be determined by measuring the frequency of fly-eye, fly-nose, fly-mouth and fly-face contacts by *Musca sorbens* after application of the product, in a 'field' environment where these flies are naturally present at high density. Control measurements will be taken of fly contact on each participant prior to this. Test measures will be repeated over a period of six hours to determine the ET_{50} , and for wearable repellent devices, participants will continue to wear the

product and tests will be repeated at one, two, three and four weeks later. Topical repellents will be applied by the Stronger-SAFE field team nurses, who will also demonstrate how to wear the repellent devices. A qualitative assessment of acceptability and barriers to use will be carried out at the end of the trial.

14 Study setting and populations

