15.4 Participant retention

Once participants are enrolled to either the laboratory or field clinical trial, both study sites will make every reasonable attempt to ensure that these participants are followed for the entire study period, when repeat observations are necessary over a duration of one month for the wearable repellent devices.

For the laboratory clinical trial, the loss-to-follow-up over this month is expected to be low, and 5 % loss-to-follow-up has been allowed for the laboratory trial sample size (+ one child). For the field clinical trial, loss-to-follow-up over that month is expected to be higher, as it may be harder to locate young children and ensure that they are at home on the required days. Therefore, a 25 % loss-to-follow-up has been allowed for the field trial sample size (+ six children). Fieldworkers at this study site will be responsible for developing and implementing local standard operating procedures to achieve this level of follow-up.

16 Interventions

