21.2.4 Wearable repellent devices

Control measurements will be taken for a ten-minute period, exactly as with the topical repellent testing, but omitting the face washing step. After this, the pre-allocated wearable repellent device will immediately be administered. Field nurses will demonstrate how to wear the repellent device, which will then be given to the participant to wear, or his/her primary caregiver to put on to the participant. The participant will then be seated again, and the videoing and observation repeated for another ten-minute period, as with the topical repellent testing. Again, the ten-minute observation period will then be repeated hourly for five further time points. After the six-hour test period, the participant will be asked to continue to wear the repellent device. The investigators will return one week later to repeat test sampling, at which point they will measure for ten minutes with the wearable repellent device still in place, then remove the device and measure for a further (control) ten minutes (Figure 8).

[figure not shown]

Figure 8. Study design for estimation of personal protection by wearable repellent devices from fly-eye contacts by *Musca sorbens*. This process will be repeated for each of 29 participants.

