29.2 Protocol amendments

A formal amendment to the protocol will be required for any protocol amendments or modifications that may impact either on the conduct of the study or may affect **participant** safety (including but not restricted to changes in: study objectives, study design, **participant** population, sample sizes, study procedures, or significant administrative aspects). Substantive¹ amendments must be reviewed and agreed by the LSHTM ethics committee prior to implementation, and will be described in trial reports. Amendments will be communicated to all relevant parties via documented (and version controlled) amendments to protocols and standard operating

¹ 'Substantive' is here defined as a protocol amendment that can affect the safety of trial participants or the scientific validity, scope, or ethical rigour of the trial

procedures. Minor amendments that have no effect on the way that the study will be conducted will be agreed by the TSC and appropriately documented.

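### The field trial's 29 children per arm allow for about 20% loss to follow-up (6 of 29), not the stated 25%

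*Combined protocol and SAP*

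**What the plan says.** Section 19.2 sizes the field trial on a difference of 30% in protective efficacy between an intervention arm and the control arm, with a standard deviation of 30% and 90% power. This gives 23 children per group. The section then adds the allowance for loss: "When allowing for 25 % loss-to-follow-up, the total sample size in each study arm will be 29 people".

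Section 15.4 repeats the percentage and gives the count behind it: "Therefore, a 25 % loss-to-follow-up has been allowed for the field trial sample size (+ six children"). The loss is expected during the month of wearable-device follow-up: "For the field clinical trial, loss-to-follow-up over that month is expected to be higher". The section goes on to make the percentage a working target: "Fieldworkers at this study site will be responsible for developing and implementing local standard operating procedures to achieve this level of follow-up".

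The summary (section 5) and sections 13.2, 21.2.3 and 21.2.4 all carry 29 per arm. The laboratory trial has a parallel statement in section 19.1, built on 16 completers: "When allowing for 5 % loss-to-follow-up, the total sample size will be 17 people".

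**The concern.** An allowance for loss to follow-up normally means that, if the stated fraction of enrolled participants is lost, the required number remains. Section 15.4 speaks of following participants once they are enrolled, so the natural denominator is the 29. Six children out of 29 is less than 25%, which suggests that the percentage was added to the completers when the completers should have been divided by the fraction retained.

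What is at stake is limited but practical. The team that writes the local procedures is asked to meet the stated level of follow-up. Working from the percentage, it could lose seven children in an arm, report that it was within plan, and still hold fewer than the 23 that section 19.2 calls for.

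**Working it through.** **Inputs.** Required completers per arm, 23 (section 19.2). Stated loss, 25% (sections 15.4 and 19.2). Children added, six (section 15.4). Enrolled per arm, 29 (section 19.2). Maximum arms, five: four products plus control (section 13.2).

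**Reproducing the plan's figure.** Completers × (1 + loss) = 23 × 1.25 = 28.75, rounded up to 29. The difference, 29 − 23 = 6, matches the count in section 15.4, so this is how 29 was obtained.

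**What 29 tolerates.** Largest loss that keeps 23 = 1 − 23/29 = 20.7%. In whole children:

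| Lost of 29 | Share lost | Remaining |
|---|---|---|
| 6 | 20.7% | 23 |
| 7 | 24.1% | 22 |
| 8 | 27.6% | 21 |

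Seven is the largest whole-number loss within 25%, and it leaves 22. At exactly 25%, 29 × 0.75 = 21.75.

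**What 25% would need.** Completers / (1 − loss) = 23 / 0.75 = 30.67, so 31; check, 31 × 0.75 = 23.25.

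**Laboratory figure, for contrast.** 16 / 0.95 = 16.84 and 16 × 1.05 = 16.8 both round up to 17, and 17 × 0.95 = 16.15, which is at least 16. The laboratory statement holds by either route, so it does not reveal which convention the authors intended.

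**Size in terms of power.** Section 19.2 states neither alpha nor sidedness. I assumed a two-sided 5% two-sample t-test with standardised difference 30/30 = 1, degrees of freedom 2n − 2 and non-centrality √(n/2). Under that assumption the unrounded requirement for 90% power is 22.02, which rounds up to the plan's 23.

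| n per arm | Power |
|---|---|
| 21.75 | 89.6% |
| 22 | 89.97% |
| 23 | 91.2% |
| 29 | 96.3% |

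The loss arithmetic does not depend on alpha; only this power table does.

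**Where the loss falls.** Section 15.4 places it in the month of device follow-up. At the weekly visits, section 21.2.4 has the investigators measure with the device on, "then remove the device and measure for a further (control) ten minutes", which is a comparison within the child. Section 13.2 says the no-product control group "will allow for temporal comparison of fly contact across a day of testing". The between-arm calculation in section 19.2 is therefore not shown to apply to the weekly visits, and I do not carry the power figures over to them.

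**The case against.** The arithmetic is not in dispute; the case on the other side is that nothing follows from it.

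- **Power.** At 22 per arm, power is 89.97% under the assumed test, in effect the planned 90%, and a normal-approximation calculation asks for only 22. This stands. No material loss of power can be claimed.
- **Timing.** Topical arms finish in one day, and section 15.3 keeps data collected up to withdrawal unless the participant asks for removal. A child lost in weeks one to four would normally still contribute first-day data, where 29 per arm gives about 96.3%. This also stands, and it limits the point to a misstated allowance.
- **The printed count.** Section 15.4 shows six children beside the 25%, so a careful reader could take six as the limit and retain exactly 23. This is partly right, but it means that the sentence carries two targets that disagree. Nothing in the documents defines the 25% as a share of the 23.
- **The remedy.** Relabelling the allowance as 20% leaves unanswered the expectation that field losses will be high. That is fair. Restating makes the text true; it does not make loss less likely. Enrolling 31 in every arm would answer it only by adding children to topical and control arms for which no month-long follow-up is described.

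**Conclusion.** The point holds. With 23 required and 29 enrolled per arm, the plan tolerates a loss of 20.7%, not 25%. At the largest whole-number loss within the stated allowance, an arm ends one child short (22 against 23).

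This rests on reading the percentage as a share of children enrolled, which is the ordinary meaning and fits section 15.4. It is an error in a stated figure that also serves as a retention target. It is not a deficiency in power: the between-arm figure falls from 91.2% to 89.97% under the assumed two-sided 5% t-test, and no loss is claimed for the weekly within-child comparison. The laboratory allowance is correct.

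**What to change.** Keep 29 per arm. In sections 15.4 and 19.2, replace the 25% with a statement that 29 allows for a loss of about 20% (6 of 29) and so retains 23. The percentage, the count of six and the field team's target then agree.

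The cost is one sentence in each of two sections, with no additional children and no change to the sample size or the trial visits. Section 29.2 provides a route for this: "Minor amendments that have no effect on the way that the study will be conducted will be agreed by the TSC and appropriately documented". The sponsor should confirm that it applies, since the written retention target becomes slightly tighter.

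If the sponsor wishes to keep 25%, the figure consistent with it is 31 per arm: up to 5 × 31 = 155 children against 5 × 29 = 145. That would mean changing every section that carries 29 and making a formal amendment, because section 29.2 lists sample sizes among the changes that require one. The size of the discrepancy does not justify this.
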